#### **8.10.6 Study Design/Dosing/Procedures Modifications Permitted Within Protocol Parameters**

The dose and administration of the study intervention to any participant may not be modified. If necessary, a participant must be discontinued for the reasons described in Section 7.

The PK/pharmacodynamic sampling scheme currently outlined in the protocol may be modified during the study based on newly available PK or pharmacodynamic data (eg, to obtain data closer to the time of peak plasma concentrations). If indicated, these collected samples may also be assayed in an exploratory manner for metabolites and/or additional pharmacodynamic markers.

Up to additional 75 mL of blood may be drawn for safety, PK, and/or pharmacodynamic analyses. The total blood volume withdrawn from any single participant will not exceed the maximum allowable volume during his/her participation in the entire study (Appendix 8).

The timing of procedures for assessment of safety procedures (eg, vital signs, ECG, safety laboratory tests, etc) may be modified during the study based on newly available data. Additional laboratory safety tests may be added to blood samples previously drawn to obtain additional safety information. These changes will not increase the number of study procedures for a given participant during his/her participation in the entire study.

It is understood that the current study may employ some or none of the alterations described above. Any alteration made to this protocol to meet the study objectives must be detailed by the Sponsor in a letter to the Study File and forwarded to the investigator for retention. The letter may be forwarded to the IRB/IEC at the discretion of the investigator.

## 9 STATISTICAL ANALYSIS PLAN

### 9.1 Statistical Analysis Plan Summary

Separately for each PK parameter, individual values of AUC0-24, Cmax, C24, AUC0-last, and AUC0-inf will be natural log-transformed and evaluated with a linear fixed effects model containing a fixed effect for population (each hepatic impairment group, and normal hepatic function). For each population, least-squares geometric means and their corresponding 95% CIs will be provided. Additionally, to compare participants with hepatic impairment to participants with normal hepatic function, a 2 sided 90% confidence interval for the true GMR (hepatic impairment/normal hepatic function) will be calculated for AUC0-24, Cmax, AUC0-last, and AUC0-inf.

The safety and tolerability of MK-8189 will be monitored by clinical assessment of adverse experiences and other safety measurements (e.g., labs, vital signs, ECGs).

### 9.2 Responsibility for Analyses

The statistical analysis of the data obtained from this study will be conducted by, or under the direct auspices of, the Early Clinical Development Statistics Department in collaboration with the Quantitative Pharmacology and Pharmacometrics Department and Translational Pharmacology Department of the Sponsor. If, after the study has begun, changes are made to the statistical analysis plan stated below, then these deviations to the plan will be listed, along with an explanation as to why they occurred, in the Clinical Study Report.

### 9.3 Hypotheses/Estimation

Part 1 Estimation: The AUC0-inf and Cmax in participants with moderate hepatic impairment will be estimated and compared to those obtained from healthy control participants.

Part 2 Estimation: The AUC0-inf and Cmax in participants with mild hepatic impairment will be estimated and compared to those obtained from healthy control participants in Part 1.

### 9.4 Analysis Endpoints

Primary Endpoints: MK-8189 PK variables (AUC0-inf and Cmax)

Secondary Endpoints: All types of adverse experiences, in addition to laboratory safety tests, 12-lead ECGs, and VS.

Exploratory Endpoints: AUC0-last, AUC0-24, C24hr, Tmax, CL/F, Vd/F and t1/2.

## 9.5 Analysis Populations

The following populations are defined for the analysis and reporting of data. All participants will be reported, and their data analyzed, according to the treatment(s) they actually received.

*All Participants as Treated:* The All Participants as Treated Population consists of all participants who received at least one dose of treatment. This population will be used for assessments of safety and tolerability.

*Per-Protocol:* The Per-Protocol Population consists of the set of data generated by the subset of participants who comply with the protocol sufficiently to ensure that these data will be likely to exhibit the effects of treatment, according to the underlying scientific model.

Compliance covers such considerations as exposure to treatment, availability of measurements and absence of important protocol deviations. Important protocol deviations will be identified to the extent possible by individuals responsible for data collection/compliance, and its analysis and interpretation. Any participants or data values excluded from analysis will be identified, along with their reason for exclusion, in the CSR.

At the end of the study, all participants who are compliant with the study procedures as aforementioned and have available data from at least one treatment will be included in the per-protocol dataset. This population will be used for the PK analysis.

## 9.6 Statistical Methods

### Pharmacokinetics:

At the end of the study, the final analysis will be run on pooled data from both study parts (if both parts are conducted).

Separately for each PK parameter, individual values of AUC0-24, Cmax, C24, AUC0-last, and AUC0-inf will be natural log-transformed and evaluated with a linear fixed effects model containing a fixed effect for population (each hepatic impairment group, and normal hepatic function). An unstructured covariance matrix will be used to allow for unequal population variances via the REPEATED and GROUP statement in SAS PROC MIXED. Kenward and Roger's method will be used to calculate the denominator degrees of freedom for the fixed effect (DDFM=KR). Ninety-five percent (95%) CIs for the least squares means for each population will be constructed on the natural log scale and will reference the t-distribution. Exponentiating the least-squares means and their corresponding 95% CIs will yield estimates for the population geometric means and confidence intervals about the geometric means on the original scale. Sample SAS code is given below:

```
proc mixed data=data;
  class population;
  model lnpk = population /ddf=kr;
  repeated/ group= population;
  lsmeans population /cl alpha=0.05;
run;
```

To compare participants in each hepatic impairment population to participants with normal hepatic function, a two sided 90% confidence interval for the true difference in means (hepatic impairment – normal hepatic function) will be calculated for AUC0-24, Cmax, AUC0-last, and AUC0-inf using the mean square error from the model and referencing a t-distribution. These confidence limits will be exponentiated to obtain the 90% confidence interval for the true ratio of geometric means (hepatic impairment/normal hepatic function) for each PK parameter and each hepatic population.

Figures showing individual PK values with GMs (95% CIs) by population, plotted on the natural log scale, will be provided for PK parameters AUC0-24, Cmax, AUC0-last, and AUC0-inf. A figure showing the GMR (hepatic impairment/normal hepatic function) and corresponding 90% CI will be provided for PK parameters AUC0-24, Cmax, AUC0-last, and AUC0-inf.

The above analyses will be carried out for PK calculated from both total and unbound concentrations.

Individual values will be listed for each PK parameter (CL/F, Vd/F, AUC0-24, AUC0-last, AUC0-inf, C24, Cmax, Tmax, fraction unbound for PK parameters (at a minimum of CL/F, Vd/F), and terminal half-life ( $t_{1/2}$ )) by population, and the following (non-model-based) descriptive statistics will be provided: N (number of participants with non-missing data), arithmetic mean, standard deviation, arithmetic percent CV (calculated as  $100 \times$  standard deviation/arithmetic mean), median, minimum, maximum, geometric mean, and geometric percent CV (calculated as  $100 \times \sqrt{\exp(s^2) - 1}$ , where  $s^2$  is the observed variance on the natural log-scale).

The relationship between MK-8189 PK and hepatic impairment will be examined in an exploratory manner via a scatter plot of PK values (AUC0-24, Cmax, AUC0-last, and AUC0-inf) versus the Child-Pugh score. Plots of PK values (AUC0-24, Cmax, AUC0-last, and AUC0-inf) and the baseline laboratory components of the Child-Pugh score (i.e., bilirubin, albumin levels, and INR time) may be provided. Plots of PK parameter values (AUC0-24, Cmax, AUC0-last, and AUC0-inf) vs age and body weight may also be provided.

Additionally, individual participant PK parameter values (AUC0-24, Cmax, AUC0-last, and AUC0-inf) may also be plotted against CrCL (estimated from Cockcroft-Gault Equation), using different symbols to identify participants from each population. Note: CrCL will be calculated as the mean of the two values determined at screening.

**Safety:** The safety and tolerability of MK-8189 will be monitored by clinical assessment of adverse experiences and other safety measurements (e.g., labs, vital signs, ECGs).

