## 9.9 Sample Size and Power Calculations

The sample size selected for each population to evaluate the effect of hepatic impairment on the PK of MK-8189 was not chosen to satisfy any a priori statistical requirement. This sample size (N=6-8 per group) has historically been shown to be sufficient for studies of this type and should provide adequate data to support the planned analyses. Nevertheless, estimates of the expected precision of the estimates, based on these sample sizes and the known variability obtained from hepatic PK studies are presented below.

The precision of the estimated ratios of geometric means (hepatic impairment / normal hepatic function) of PK parameters obtained from this study can be assessed by calculating the half-width of the 90% CIs expected for the given sample size and assumed variability. The pooled between-subject standard deviation (on the natural log scale) for AUC0-24 in participants with normal hepatic function and participants with schizophrenia on 4 mg MK-8189 was 0.29  $\ln(nM^{\ast}hr)$  from P003. The pooled between-subject standard deviation for AUC0-24 was obtained using the between subject standard deviation of 0.16  $\ln(nM^{\ast}hr)$  in healthy and between subject deviation of 0.39  $\ln(nM^{\ast}hr)$  in participants with schizophrenia on 4 mg MK-8189 in P003. The variability for AUC0-inf in participants with moderate hepatic impairment is assumed to be similar to the variability in AUC0-24 in participants with schizophrenia for 4 mg dose from P003. The variability for AUC0-inf in participants with normal hepatic function is assumed to be similar to the variability in AUC0-24 in healthy participants for 4 mg dose from P003. Assuming a minimum sample size of 6 participants per population and observed between-subject standard deviation as given above, then the half width of the 90% CIs of GMRs for MK-8189 AUC0-inf on the log scale will be 0.30. The lower and upper 90% confidence limits for the true GMRs will be given by  $OBS/1.35$  and  $OBS*1.35$  for AUC0-inf, where OBS is the observed GMR. Thus, for example, if the observed GMR for AUC0-inf was 1.50, then the 90% CI for the GMR would be 1.11 to 2.03.

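### Section 9.6 fits a separate variance for each group but bases the primary 90% CI on a mean square error that this model does not produce

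*Combined protocol and SAP*

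**What the plan says.** Section 9.6 of the combined protocol and SAP describes the fitted model as follows: "An unstructured covariance matrix will be used to allow for unequal population variances via the REPEATED and GROUP statement in SAS PROC MIXED". The sample code carries this out with "repeated/ group= population", and the text names Kenward-Roger degrees of freedom.

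After the code, a separate paragraph defines the 90% interval for each impaired-minus-normal difference on the log scale. It is to be obtained "using the mean square error from the model and referencing a t-distribution" and exponentiated to give the interval for the geometric mean ratio (GMR). The degrees of freedom are not named there.

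The last modelling line of the code is "lsmeans population /cl alpha=0.05", which returns 95% intervals for the group means only. Section 9.6 also states: "At the end of the study, the final analysis will be run on pooled data from both study parts", if both parts are conducted. One model may therefore hold three populations.

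Section 9.9 gives the expected precision at 6 per group: "then the half width of the 90% CIs of GMRs for MK-8189 AUC0-inf on the log scale will be 0.30". That is a factor of 1.35, or 1.11 to 2.03 at an observed GMR of 1.50.

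**The concern.** A mean square error is the common residual variance of an equal-variance model. With a separate variance for each population, the fit returns two or three residual variances and no common one. The sentence defining the primary interval therefore names a quantity that the specified model does not yield. Two analysts could follow the section in good faith and report different intervals from the same data: one from the fitted group variances, the other from a pooled variance.

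The choice matters because the plan expects the variances to differ about six-fold: (0.39/0.16)² = 5.9. A pooled interval can then be too narrow or too wide, depending on the group sizes. In the three-group analysis it also depends on the variance of the mild group, which has no bearing on the moderate-versus-healthy comparison. The GMR point estimates and the 95% intervals for the group means are not affected.

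**Working it through.** **Inputs.** From section 9.9: log-scale SD 0.16 in healthy participants, 0.39 for moderate impairment (borrowed from participants with schizophrenia), pooled SD 0.29, and 6 per group. From Table 2: 6 to 8 per group. The documents give no SD for mild impairment, so 0.16 to 0.39 is assumed. They give none for Cmax, so sizes are shown for AUC only.

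**The plan's figure, reproduced as a pooled interval.** Half-width = t(0.95, 10) × 0.29 × √(2/6) = 1.812 × 0.1674 = 0.303. The factor is 1.35, and the interval at a GMR of 1.50 is 1.11 to 2.03. This matches section 9.9.

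**The same quantity under the specified model.** For this group-means model the Kenward-Roger degrees of freedom reduce to Satterthwaite's.

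- SE = √((0.16² + 0.39²)/6) = √(0.1777/6) = 0.172
- df = 5 × 0.1777² / (0.0256² + 0.1521²) = 6.64
- Half-width = 1.910 × 0.1721 = 0.329; factor 1.39; interval at 1.50 is 1.08 to 2.08

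Part of the gap comes from the SD. The root mean square of 0.16 and 0.39 is 0.298, not 0.29, and 0.298 with 10 df gives 0.312. The rest, from 0.312 to 0.329, comes from the degrees of freedom.

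**Unequal group sizes, Part 1 only.** Pooled half-width = t(0.95, n₀+n₁−2) × s_p × √(1/n₀ + 1/n₁).

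| Healthy / moderate | Pooled SD | Pooled half-width | Separate-variance half-width (df) |
|---|---|---|---|
| 8 / 6 | 0.280 | 1.782 × 0.280 × 0.540 = 0.269 | 0.326 (6.27) |
| 6 / 8 | 0.315 | 1.782 × 0.315 × 0.540 = 0.304 | 0.277 (9.80) |

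**Three groups, 6 each.** The common MSE is (0.16² + 0.39² + s²)/3 on 15 df, where s is the mild SD. For s = 0.16 / 0.29 / 0.39 the pooled half-width is 0.264 / 0.299 / 0.336 for both comparisons. With separate variances, moderate versus healthy stays at 0.329, and mild versus healthy is 0.167 / 0.252 / 0.329.

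**Coverage of the nominal 90% interval when a pooled MSE is used.** Simulated with normal group means and chi-square group variances, 1,000,000 runs per scenario.

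| Part 1, healthy / moderate | 6/6 | 8/8 | 8/6 | 6/8 |
|---|---|---|---|---|
| Coverage | 88.7% | 89.1% | 85.0% | 92.2% |

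| Three groups, 6/6/6, by mild SD | 0.16 | 0.27 | 0.31 | 0.39 |
|---|---|---|---|---|
| Moderate vs healthy | 84.0% | 88.4% | 89.9% | 92.4% |
| Mild vs healthy | 98.2% | 95.7% | 94.6% | 92.5% |

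Over all eight combinations of 6 or 8 per group, moderate versus healthy runs from 79.2% (8 healthy, 6 moderate, 8 mild, mild SD 0.16) to 94.8% (6, 8, 8, mild SD 0.39). Mild versus healthy runs from 89.7% to 98.9%. The separate-variance interval stays between 89.7% and 90.5% throughout.

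**The case against.** The strongest reply is that section 9.6 specifies only one model, so an error term taken from the model can only mean that model's group variances. On this reading the phrase is loose and the interval is sound. A later refit with equal variances would be a change to the plan, and section 9.2 requires such changes to be listed and explained in the study report. The code is labelled as a sample and does produce the 95% intervals that it follows. Section 9.9 is a planning approximation that openly uses a pooled SD, and the sample size was not derived from it.

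Much of this is fair. If the contrast is taken from the specified fit, coverage is about 90% and there is no error. In Part 1 at equal sizes, even a pooled interval loses only about one point. The widest departures need Part 2 to run, unequal groups and an assumed mild SD. The study tests no hypothesis, and no confidence limit is tied to the decision on Part 2.

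The reply does not settle which reading is meant. The only place where the plan works out this interval, section 9.9, uses the pooled form. It can also be said that the average half-width over repeated samples at 6 per group is about 0.32 rather than 0.33. But section 9.9 takes the stated SDs as the observed ones, so 0.33 is the like-for-like figure.

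**Conclusion.** The point holds. Section 9.6 specifies group-specific variances and then defines the primary 90% interval through an error term that exists only with a common variance. Nothing else in the documents resolves this.

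The practical effect depends on which reading is used. With the fitted model there is none. With a pooled error, the effect in Part 1 is about one percentage point of coverage at equal sizes, and about five points below or two above nominal when the groups are 8 and 6. It is larger in the three-group analysis, where the direction for moderate impairment at equal sizes turns at a mild SD of about 0.31. These sizes rest on the section 9.9 SDs for AUC, on normality on the log scale and, for three groups, on the assumed mild SD.

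Separately, the precision stated in section 9.9 does not match the specified model. This should be fixed before analysis; it is no threat to the design.

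**What to change.** In section 9.6, replace the reference to the mean square error with wording such as: *using the difference in least-squares means, its standard error from the group-specific residual variances, and Kenward-Roger degrees of freedom*.

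In the sample code, change `ddf=kr` to `ddfm=kr` to match the text. Add an `LSMEANS` difference or an `ESTIMATE` statement comparing each impaired group with normal hepatic function, with `CL` and `alpha=0.10`.

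In section 9.9, restate the precision at 6 per group as a half-width of about 0.33, a factor of 1.39, and an interval of about 1.08 to 2.08 at a GMR of 1.50.

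If the sponsor does intend a common variance, the plan should say so, remove the `GROUP=` option and accept the coverage shown above. The separate-variance form is preferable because it holds its nominal level across the planned group sizes.

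The cost is one sentence and two code lines in 9.6 and the precision figures in 9.9. There is no operational cost and no change to the sample size.

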Part 1 and Part 2 

To investigate the relationship between CYP2C9 genetic polymorphisms and the PK of MK-8189. Genetic variation in CYP2C9 may be analyzed for association with any laboratory or clinical data collected in this study.

To explore the relationship between genetic variation and response to the treatment administered, and mechanisms of disease. Variation across the human genome may be analyzed for association with clinical data collected in this study.

To compare additional MK-8189 pharmacokinetic parameter values after single dose administration of 4 mg MK-8189 to participants with moderate hepatic impairment, mild hepatic impairment, and healthy control participants.

	Part 1 and Part 2 

Germline genetic variation in CYP2C9 and association to clinical data collected in this study

Germline genetic variation and association to clinical data collected in this study.

AUC0-24, C24, Tmax, CL/F, Vz/F and apparent terminal <math>t_{1/2}</math>

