### 4.2.1.2 Pharmacokinetic Endpoints

An objective of this study is to characterize the PK of MK-8189 in participants with hepatic impairment. Therefore, individual plasma concentration and actual sample collection times of MK-8189 will be used to derive the PK parameter values such as AUC0-24, AUC0-inf, Cmax, Tmax, C24hr, CL/F, Vd/F and apparent t1/2. Protein binding for MK-8189 will also be analyzed. As MK-8189 is highly protein bound, the fraction unbound PK parameters (at a minimum CL/F, Vd/F) will be provided in healthy participants and participants with hepatic impairment.

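### Does the plan need to say whether the primary AUC0-inf and Cmax ratios are total or unbound?

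*Combined protocol and SAP*

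**What the plan says.** Section 9.4 lists "Primary Endpoints: MK-8189 PK variables (AUC0-inf and Cmax"). Its exploratory line reads "Exploratory Endpoints: AUC0-last, AUC0-24, C24hr, Tmax, CL/F, Vd/F and t1/2". Section 9.3 states the Part 1 aim as "The AUC0-inf and Cmax in participants with moderate hepatic impairment will be estimated and compared" with healthy controls, and words Part 2 in the same way for mild impairment. The exploratory PK row in Section 3 reads "AUC0-24, C24, Tmax, CL/F, Vz/F and apparent terminal" half-life. None of these mentions unbound drug.

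Unbound PK appears in three other places:
- Section 4.2.1.2 says that "the fraction unbound PK parameters (at a minimum CL/F, Vd/F) will be provided in healthy participants and participants with hepatic impairment".
- The descriptive listing in Section 9.6 includes "fraction unbound for PK parameters (at a minimum of CL/F, Vd/F").
- The modelling part of Section 9.6 ends: "The above analyses will be carried out for PK calculated from both total and unbound concentrations".

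That last sentence covers the GMRs and 90% CIs for AUC0-24, Cmax, AUC0-last and AUC0-inf. Section 9.8 states that there is no hypothesis testing.

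**The concern.** A primary endpoint should identify one quantity. Read literally, Section 9.6 produces two AUC0-inf GMRs and two Cmax GMRs for each comparison, and the endpoint list does not say which pair is primary. The floor of unbound CL/F and Vd/F in Section 4.2.1.2 also looks narrower than the modelling commitment in Section 9.6.

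Binding could matter for this drug. Section 2.2.2.1 gives a human unbound fraction of 4.0%, and low albumin is one route to the laboratory-score requirement in Section 5.1.2. If the fraction unbound rises with impairment, the unbound GMR exceeds the total GMR, and a sponsor who has seen both could pick the headline. Sections 4.1 and 4.2 make Part 2 depend on a clinically meaningful rise in exposure, again without saying which version.

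**Working it through.** **1. The plan's own precision figure.** Inputs from Section 9.9: n = 6 per group, pooled SD 0.29 on the log scale, 90% two-sided CI.

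Half-width = t(0.95, 10 df) × SD × √(2/n) = 1.812 × 0.29 × √(2/6) = 0.303, stated as 0.30. The factor is exp(0.303) = 1.35. For an observed GMR of 1.50 this gives 1.11 to 2.03, which matches "if the observed GMR for AUC0-inf was 1.50, then the 90% CI for the GMR would be 1.11 to 2.03". The figure is not in dispute.

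**2. How the two versions are linked.** The schedules in Sections 1.3.1 and 1.3.2 take one predose binding sample per participant. If that single fraction unbound (fu) is applied throughout, unbound AUC = fu × total AUC, and likewise for Cmax. In the same participants,

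unbound GMR = total GMR × (geometric mean fu, impaired ÷ healthy).

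The two results therefore differ by one observable factor.

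**3. How far apart they could be.** The documents give no fu for hepatic impairment, so the fu ratios are assumptions. If the total GMR is 1.50:

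| Assumed fu ratio | Unbound GMR |
|---|---|
| 1.0 | 1.50 |
| 1.25 | 1.88 |
| 1.5 | 2.25 |
| 2.0 | 3.00 |

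The direction of reading matters. Applying the 1.35 factor to both versions at an fu ratio of 1.25:
- If 1.50 is the total GMR, its CI is 1.11 to 2.03. The unbound GMR is 1.88, CI 1.88/1.35 to 1.88 × 1.35 = 1.39 to 2.53. Both exclude 1.0.
- If 1.50 is the unbound GMR, the total GMR is 1.50/1.25 = 1.20, CI 1.20/1.35 to 1.20 × 1.35 = 0.89 to 1.62. Only one excludes 1.0. On this reading the total CI reaches 1.0 once the fu ratio passes 1.50/1.35 = 1.11.

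Section 9.9 builds its example on unqualified AUC standard deviations, so the first reading fits the text better.

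**4. How often the intervals would disagree.** Simulation with 200,000 trials per setting, n = 6, SDs 0.16 and 0.39, Welch 90% CIs, and an assumed SD of ln fu of 0.10 or 0.20. The share of trials in which exactly one interval excludes 1.0, at an fu ratio of 1.25, is about 33–49% if the true unbound GMR is 1.5 and about 21–39% if the true total GMR is 1.5. With no shift in fu it is still 10–21%, from fu noise alone. The plan attaches no decision to excluding 1.0.

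**5. Which version the text means.** Section 4.2.1.2 first derives plain AUC0-inf, Cmax and the rest from plasma concentrations, then introduces binding as an addition, then names the unbound parameters separately. The Section 9.6 listing makes the same split. The schedules have separate rows for plasma MK-8189 and for plasma protein binding. In each place the unqualified name is total and the unbound version carries a qualifier.

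**6. Whether the scopes conflict.** The CL/F and Vd/F commitment is a floor, and the modelling sentence goes above it. With a fixed 4 mg dose, unbound CL/F = dose ÷ unbound AUC0-inf, so the floor already carries the unbound AUC0-inf information. Unbound Cmax is the main addition.

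**The case for a change.** The strongest case for a change is that Amendment 01 was written partly to clarify the primary endpoints, yet two quantities still share each primary name. The label would cost a few words and no extra blood, since the binding sample is already in Appendix 8. Convention favours total, but no sentence says so, and the last modelling sentence of Section 9.6 puts the two versions side by side.

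The textual observation stands: the label and the tier are absent. The consequence does not follow. A selective headline would need one version to be withheld, and Section 9.6 commits the sponsor to both. Open-label conduct adds nothing, because every group takes the same single dose and blinding would not hide either GMR from the analyst.

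The Part 2 argument is weaker still. The decision is a Sponsor judgement after review of the Part 1 safety and PK data, with no numeric threshold for a lead version to feed. Nothing excludes unbound results from that review, and Section 4.4 allows a pause for further data. Requiring them would make an optional preliminary analysis wait for the binding assay.

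**Conclusion.** No change follows. The endpoint list omits a word that Section 4.2.1.2 and the layout of Section 9.6 supply: primary AUC0-inf and Cmax are total, and the unbound versions are reported alongside. No type I error is at stake, no planned estimate or interval would change, and the precision statement of 0.30 is unaffected. The gap between the versions may be material, for example 1.50 against 1.88 at an assumed fu ratio of 1.25, but both would be in the report and their ratio shows the binding effect directly. This rests on Section 9.6 being carried out as written, so that both versions are reported, and on total being the intended default, which the text implies without stating.
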